#### **3.2.1. Primary Aim 1: To test that NTX and VAR will reduce drinking during the practice quit attempt as compared to placebo.**

A series of repeated measures ANCOVAs will be conducted using PROC GLM in SAS Statistical Software. Specifically, we will conduct repeated measures ANCOVAs on Percent Days Abstinent (PDA), and Drinks per Drinking Day (DPDD), our two co-primary outcomes, as predicted by Medication (NTX vs. PLAC and VAR vs. PLAC) a between-subjects factor and the covariate of baseline PDA and DPDD.

#### **3.2.2. Primary Aim 2: To test that NTX and VAR will reduce cue-induced craving for alcohol as compared to placebo.**

We will conduct a series of repeated measures ANOVAs on Alcohol Cue – Water Cue change scores on the AUQ as predicted by Medication condition (NTX vs. PLAC and VAR vs. PLAC).

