### **2.4. Established medication should be used to test a novel model.**

Naltrexone is the most widely studied of the FDA-approved medications for AUD. NTX is an opioid antagonist, with the highest affinity for the mu-opioid receptor. The neurobiological basis for the use of NTX stems from the neurocircuitry through which alcohol exerts its effects [28, 29]. Alcohol increases release of endogenous opioids in the mesolimbic dopamine system contributing to the pleasurable effects of alcohol [28, 29], thus an opioid antagonist is proposed to block these reinforcing effects. Oral NTX was approved by the FDA in 1994 after initial trials suggested that NTX resulted in significantly fewer drinking days and lower rates of relapse, defined as drinking 5 or more drinks on an occasion for men or four or more drinks on an occasion for women (23% relapse rate for NTX versus 54% relapse rate for placebo) following three months of treatment [30, 31]. These initial results have been largely supported by more recent trials of NTX that have generally demonstrated NTX reduces the subjective pleasurable effects of alcohol [32, 33], craving for alcohol [34, 35], drinks per drinking day [36], rates of relapse [37, 38], and time to first relapse [39, 40]. However, the support for NTX is not uniform. A few trials, including a large multisite trial, have reported no significant outcome differences between NTX and placebo treated patients [41-43]. Moreover, the effect sizes of previous findings are often modest even when they reach statistical significance. Extended-release injectable NTX was developed to address poor medication adherence with oral NTX [44]. A multi-site trial of long-acting NTX identified significant reductions in the number of heavy drinking days over a period of 6 months compared to placebo [45]; however this effect was only significant for men [45]. Improvements in drinking outcomes were greater in individuals who were abstinent for at least 4 days prior to randomization [45, 46]. In sum, studies of NTX suggest a moderate effect on the reduction of alcohol use. While we considered using a novel compound and are aware that new studies of NTX are not encouraged by NIAAA, we agree with the comments of the reviewers which argued for the use of an established medication to test the novel paradigm. As such, we propose to use NTX in this study. We would like to clarify that this is not a NTX study per se, but instead is a study of a novel experimental approach to screen pharmacotherapies for AUD and that NTX is used simply because it is a well-known medication, ideal for testing a novel paradigm.

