## **3. STUDY OBJECTIVES**

### **3.1. Specific Aims**

Primary Aim #1: To test whether NTX (50 mg) or VAR (2 mg) results in a (a) higher percentage of days abstinent and (b) lower number of drinks per drinking day during the 7-day practice quit attempt, as compared to placebo.

Primary Aim #2: To test whether NTX (50 mg) or VAR (2 mg) reduces cue-induced craving for alcohol, as compared to placebo. This aim allows us to confirm NTX effects using an established and widely studied paradigm.

Primary Aim #3: In order to validate this early efficacy paradigm, we will test the association between medication effects on cue-reactivity in the laboratory and drinking behavior during the practice quit attempt.

Secondary Aim #1: To determine whether the effects of medication on the multiple-choice paradigm are mediated by changes in discounting or demand for alcohol.

[figure not shown]
Secondary Aim #2: To determine whether the number of drinks per drinking day and percentage of days abstinent during the practice quit attempt predict alcohol choice.

Exploratory Aim: In order to test medication efficacy, we will directly compare NTX and VAR on percentage days abstinent and number of drinks per drinking day during the 7-day practice quit attempt.

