## 4. STUDY DESIGN

### 4.1. Design Overview

This study design consists of a randomized, double-blind, placebo-controlled, 3-arm, parallel-group study of naltrexone (50 mg QD) and varenicline (1 mg BID). A total of 108 men and women with current AUD (moderate or severe) and reporting intrinsic motivation to change their drinking, will be randomly assigned to receive naltrexone (50 mg QD), varenicline (1 mg BID) or matched placebo. Post-randomization, all participants will complete an alcohol cue-reactivity paradigm prior to the initial dose of study medication. After a week-long medication titration period, participants will be asked to come in to the laboratory to receive their second medication blister pack and to begin a 7-day practice quit attempt, during which they will have daily virtual (online and phone) visits where they will report on their alcohol use. Additionally, a second cue-reactivity paradigm will be conducted 90 minutes after study drug administration, followed by a behavioral economics paradigm on the final day of the practice quit attempt (Day 14).

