#### 5.4.4. Alcohol Cue Reactivity Sessions (CR)

Randomized participants will complete a cue-exposure paradigm at two time points during the study, once on Day 1 prior to ingesting the first dose of study medication, and again on Day 14, approximately 90 minutes after study drug administration. Alcohol cue exposure will follow well-established experimental procedures. Sessions will begin with a 3-minute relaxation period. Participants will then hold and smell a glass of water for 3 minutes to control for the effects of simple exposure to any potable liquid. Next, participants will hold and smell a glass of their preferred alcoholic beverage for 3 minutes. Order is not counterbalanced because of carryover effects that are known to occur. Participants (who are smokers) will be allowed a smoke break immediately prior to the CR assessment. After every 3 minutes of exposure, participants will rate their urge to drink on the Alcohol Urge Questionnaire (AUQ) and their mood on the Profile of Mood States (POMS). AUQ score (alcohol minus water) is the primary outcome for the CR.

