### **3. STATISTICAL METHODS AND POWER CONSIDERATIONS**

#### **3.1. Statistical Power**

Power analyses were conducted using G\*Power 3.1.9.2. In order to conduct a one-way ANOVA with fixed effects, we estimated a medium-to-large effect size ( $f=0.40$  and an alpha error probability of 0.05). Specifically, with 3 groups a sample size of 90 completers, the proposed

study has an actual power of 0.91%. Therefore, we propose to randomize 108 individuals (36 in each group) to reach a final sample of 30 completers per group. This will allow us the statistical power to detect a medium-to-large effect size as projected.

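### Aim 2 leaves the cue session and the tested term unstated; a Day 14 ANCOVA on the pre-dose Day 1 score would settle both and be at least as precise, at almost no cost

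*Combined protocol and SAP*

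**What the plan says.** Primary Aim 2 (Specific Aims) asks whether naltrexone or varenicline "reduces cue-induced craving for alcohol, as compared to placebo". Section 5.4.4 schedules the cue session "once on Day 1 prior to ingesting the first dose of study medication, and again on Day 14", and the Design Overview confirms that "all participants will complete an alcohol cue-reactivity paradigm prior to the initial dose of study medication". The outcome is defined as "AUQ score (alcohol minus water) is the primary outcome for the CR", with no session named.

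The analysis in section 3.2.2 is one sentence: "repeated measures ANOVAs on Alcohol Cue – Water Cue change scores on the AUQ as predicted by Medication condition", with the two active-versus-placebo contrasts in brackets. It names no session factor, no interaction and no covariate. The covariate list in section 3.2 is open-ended and does not include Day 1 AUQ reactivity. By contrast, section 3.2.1 gives the Aim 1 model medication as "a between-subjects factor and the covariate of baseline PDA and DPDD". The power section describes a different model: "In order to conduct a one-way ANOVA with fixed effects".

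**The concern.** Taking alcohol minus water already removes cue type as a repeated factor. The phrase about repeated measures therefore suggests that both sessions enter, yet medication is the only predictor named. Three analyses could be run under this text:

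- **Medication by session:** tests whether the change from Day 1 to Day 14 differs by arm. Valid.
- **Day 14 only:** repeated measures would then refer loosely to the alcohol/water pair. Valid, and in line with the one-way ANOVA used for power.
- **Medication main effect over both sessions:** averages in a session that no drug can have affected.

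None of the three uses the Day 1 score as a covariate. Aim 2 is a primary aim and serves to confirm naltrexone effects in an established paradigm. Section 3.2.3 also takes its cue-reactivity measure from Aim 2. At stake are a defined primary test and some precision that is available from data already collected.

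**Working it through.** **The plan's own figure.** One-way ANOVA, three groups, f=0.40, alpha 0.05, 90 completers: noncentrality 0.40² × 90 = 14.4 on 2 and 87 df gives power 0.926. The plan states 0.91 (printed with a percent sign); 84 completers would give 0.907. The figure reproduces closely enough, but it is for an omnibus test without a baseline or a repeated measure, and it is not tied to the AUQ.

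**Inputs.** From the Statistical Power section: 30 completers per arm, alpha 0.05, f=0.40. Assumed: f=0.40 applies to the Day 14 AUQ score; Day 1 and Day 14 SDs are equal; the correlation r between sessions is 0.3, 0.5 or 0.7; arms have equal expected scores on Day 1, as randomization implies.

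**From f to d.** With two arms sharing a mean, d = 0.40 × 3/√2 = 0.85. With evenly spaced means (−a, 0, a), a√(2/3) = 0.40, so a = 0.49 and the pairwise differences are 0.98 and 0.49. The d=0.5 rows below therefore also stand, nearly, for the smaller contrast under even spacing.

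**Effect and per-participant variance v** (Day 14 SD = 1):

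- Medication by session: effect d, v = 2(1 − r)
- Day 14 only: effect d, v = 1
- Day 14 ANCOVA on Day 1: effect d, v = 1 − r²
- Main effect over both sessions: effect d/2, v = (1 + r)/2

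Power comes from the noncentral t with noncentrality effect/√(2v/30) and 87 error df (86 for ANCOVA). Example at r=0.3, d=0.85: medication by session has v = 1.4 and noncentrality 2.78; ANCOVA has v = 0.91 and noncentrality 3.44.

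| Power per contrast | r=0.3 | r=0.5 | r=0.7 |
|---|---|---|---|
| d=0.85, medication by session | 0.78 | 0.90 | 0.99 |
| d=0.85, Day 14 only | 0.90 | 0.90 | 0.90 |
| d=0.85, ANCOVA | 0.93 | 0.96 | 0.995 |
| d=0.85, main effect | 0.52 | 0.47 | 0.42 |
| d=0.5, medication by session | 0.37 | 0.48 | 0.70 |
| d=0.5, Day 14 only | 0.48 | 0.48 | 0.48 |
| d=0.5, ANCOVA | 0.52 | 0.60 | 0.77 |

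Completers per arm for 80% power at d=0.5: medication by session 89/64/39, Day 14 only 64, ANCOVA 58/48/33.

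**Why ANCOVA does not depend on guessing r.** Its variance relative to medication by session is (1 − r²)/(2(1 − r)) = (1 + r)/2, that is 35%/25%/15% lower. Relative to Day 14 only it is r² lower, that is 9%/25%/49%. If the Day 1 SD is k times the Day 14 SD, the medication-by-session variance exceeds the ANCOVA variance by (1 + k² − 2rk) − (1 − r²) = (k − r)², which is never negative. With k=1.25, medication-by-session power at d=0.85 is 0.68/0.81/0.95; with k=0.8 it is 0.86/0.94/0.995. ANCOVA is unchanged in both cases.

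**The case against.** The best defence is that the plan is less open than it looks. With one session before drug and one on drug, and an aim about reducing craving, a statistician would read section 3.2.2 as medication by session, which is valid. The covariate list does not exclude the Day 1 score. At the planning effect the gain can be small: under 3 points over Day 14 only at r=0.3, and under 1 point over medication by session at r=0.7. The remark in section 2.4 that "the effect sizes of previous findings are often modest even when they reach statistical significance" concerns naltrexone findings in general. It gives no AUQ effect size and does not cover varenicline. At d=0.5 ANCOVA itself stays below 80% power at all three correlations.

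All of that stands, and it limits the point to an improvement. It does not remove the gap, because the sentence still names neither the session nor the term.

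A reader might infer three stronger claims that the documents do not support:

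- **That Aim 2 has about half the power it needs.** The figures of 0.42 to 0.52 belong only to the main effect over both sessions, which the wording permits but which is the least natural reading.
- **That the baseline is thrown away.** This is true only of the Day 14-only test. Medication by session uses Day 1 as a repeated measure; it is just not used as a covariate.
- **That type I error is inflated.** That would require the test to be chosen after the results are seen, and nothing in the documents says so. Each test, fixed in advance, holds close to 0.05 in simulation.

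**Conclusion.** The point holds as a free improvement. The plan for a primary aim leaves the session, the tested term and the baseline covariate unstated. The two valid readings are each less precise than Day 14 ANCOVA at any correlation strictly between 0 and 1 with equal SDs, apart from one degree of freedom. Against the most sensible reading, medication by session, the gain per contrast at d=0.85 is about 14, 6 and 1 percentage points at r=0.3, 0.5 and 0.7. At d=0.5 it is about 15, 12 and 7 points.

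These sizes rest on a correlation that the documents do not give, on applying f=0.40 to the AUQ, and on one pattern of means for d=0.85. The direction rests on none of these: ANCOVA is at or near the best of the options whatever the correlation.

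**What to change.** Replace the Aim 2 model in section 3.2.2 with an ANCOVA of the Day 14 alcohol-minus-water AUQ score on treatment, with the Day 1 alcohol-minus-water score as covariate, testing naltrexone versus placebo and varenicline versus placebo. In section 5.4.4, state that the primary cue-reactivity outcome is the Day 14 score.

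The cost is a change of wording and one error degree of freedom (87 to 86). Both sessions are already scheduled for every randomized participant, so no new data are needed. The change does not settle multiplicity across the two contrasts, missing Day 14 sessions or how Aim 3 forms its drug-minus-placebo scores; those need their own text.

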#### **3.2.3. Primary Aim 3: To test that medication effects on cue-reactivity are associated with medication effects on drinking outcomes during the quit attempt.**

A series of regression analyses will be conducted testing whether medication effects on drinking (indicated by NTX – PLAC and VAR – PLAC change scores) are predicted by medication effects on cue reactivity (indicated by NTX – PLAC and VAR – PLAC change scores on the cue reactivity outcomes described for Aim #2).

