### 5.4. Medication Phase

#### 5.4.1. Randomization and Medication Titration

Participants who are eligible after the physical exam will be randomized to one of three treatment conditions (VAR, NTX, or PLA). Urn randomization will be used to balance the groups by gender, smoking status (as reported on question 1 of the Fagerstrom Test for Nicotine Dependence), and drinking status ('heavy' drinker defined as 14 or more drinks per week for

males/7 or more drinks per week for females, or 'very heavy' drinker, defined as 35 or more drinks per week for males/28 or more drinks per week for females). The UCLA Research Pharmacy will manage the blind. The three treatment conditions will not be different in appearance or method of administration. All participants will undergo a week-long medication titration period prior to the onset of the practice quit attempt.

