### **3.2. Data Analytic Plan**

Descriptive statistics will be computed for continuous outcome variables, and frequencies for categorical variables to summarize the study data. Box plots, histograms, and Q-Q plots will be used to check for skewness and normality for continuous variables. Transformations of continuous outcome variables will be performed as necessary to ensure that the normality assumptions in parametric tests are met. The models described below will test whether medication effects in reducing drinking behavior during the practice quit attempt are associated with concurrent blunting of cue reactivity. To improve model fit and hypothesis testing, we will consider covariates, such as age, sex, ethnicity, medication order, and AUD symptom count.

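### Primary Aim 3 is built on drug-minus-placebo scores that no participant in this parallel-group trial has, and the readings that can be computed do not answer the aim

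*Combined protocol and SAP*

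**What the plan says.** Specific Aims (section 3.1 of Study Objectives) lists this as a primary aim and gives it a validating role: "In order to validate this early efficacy paradigm, we will test the association between medication effects on cue-reactivity" and drinking in the quit week.

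The analysis is in section 3.2.3 of the statistical methods. A series of regressions will test whether "medication effects on drinking (indicated by NTX – PLAC and VAR – PLAC change scores) are predicted by medication effects on cue reactivity", the latter expressed as the same two drug-minus-placebo change scores on the Aim 2 outcomes. The cue-reactivity measure is defined in section 5.4.4: "AUQ score (alcohol minus water) is the primary outcome for the CR".

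The design is stated in section 4.1: "This study design consists of a randomized, double-blind, placebo-controlled, 3-arm, parallel-group study". Section 5.4.1 says that eligible participants "will be randomized to one of three treatment conditions (VAR, NTX, or PLA"). Section 3.2.1 (Primary Aim 1) models the outcomes "as predicted by Medication (NTX vs. PLAC and VAR vs. PLAC) a between-subjects factor", and section 3.2.2 (Primary Aim 2) models the AUQ scores "as predicted by Medication condition (NTX vs. PLAC and VAR vs. PLAC").

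The introduction to the Data Analytic Plan (section 3.2 of the statistical methods) gives the general intent, that drug effects on drinking "are associated with concurrent blunting of cue reactivity". It also lists medication order among the covariates to be considered.

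**The concern.** A drug-minus-placebo change score for a person requires that person to be observed on both drug and placebo, as in a crossover. Here each person is observed on one treatment only. Medication order as a covariate has the same problem: nobody receives treatments in an order.

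In Aims 1 and 2 the drug–placebo pairings are levels of a predictor, which suits a parallel trial. In Aim 3 they become values of both the outcome and the predictor. A contrast between arms can be a regression coefficient, but it cannot be a participant's outcome value.

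At stake is the aim that is meant to validate the paradigm. If the section stays as it is, someone must choose a model after the fact, and the candidates answer different questions. In particular, an ordinary correlation between craving and drinking could be reported as if it showed that drug effects in the laboratory track drug effects on drinking.

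**Working it through.** **Inputs.** Three arms, one treatment each (sections 4.1 and 5.4.1); 108 randomized, 36 per arm, and 90 completers, 30 per arm (section 3.1, Statistical Power); alpha 0.05 (same section); cue sessions on Day 1 before dosing and on Day 14 (section 5.4.4); quit week from Day 8 (section 5.4.2). The documents give no craving–drinking correlation, so the values below are assumptions.

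**The plan's own figure.** The only power statement is for a one-way ANOVA with f = 0.40 and 90 completers. Noncentrality is 90 × 0.40² = 14.4 on 2 and 87 df, which gives power 0.926. The plan prints 0.91%; read as 0.91, that agrees within 2 points. The completer count also follows: 108 × 30/36 = 90. Neither figure concerns Aim 3.

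**Reading 1: a score within each person.** Treatments per participant = 1, so 0 of 108 participants have the score.

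**Reading 2: contrasts between arms.** Each outcome pair gives two points, NTX – placebo and VAR – placebo.
- With an intercept, residual df = 2 − 2 = 0. The fit is perfect whatever the data, and there is no p-value. The slope is [(yN − yP) − (yV − yP)] / [(xN − xP) − (xV − xP)] = (yN − yV) / (xN − xV). The placebo arm cancels and only NTX versus VAR remains. With no true association the slope is positive in about 50% of simulated trials.
- Through the origin, 1 df remains and placebo stays in the slope. One df is still useless for inference.
- A series of regressions adds more two-point fits, not more points to any fit.

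**Reading 3: the three arm means.** Residual df = 3 − 2 = 1. The critical t is 12.706, so the critical |r| = 12.706 / √(12.706² + 1) = 0.997.

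**Reading 4: each active participant's score minus the placebo-arm mean.** The same constant is taken from every score, so the slope is unchanged; in a numerical check it was −0.0035 before and after. Within a drug arm this is the ordinary craving–drinking association. If the drugs are pooled without an arm term, any NTX–VAR difference in means also enters. Simulated share of trials with p<0.05 when neither drug has any effect:

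| Assumed r | Pooled, n = 60 | Per drug, n = 30 |
|---|---|---|
| 0.2 | about 34% | about 18% |
| 0.3 | about 65% | about 37% |
| 0.4 | about 90% | about 60% |

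Separate simulation runs differ by about 1 point. The section does not say whether to pool.

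**What a participant-level model could detect.** With an intercept, Day 14 AUQ, Day 1 AUQ, baseline drinking and two arm terms there are 6 coefficients, so residual df = 90 − 6 = 84. The Fisher approximation for 80% power is r = tanh[(1.960 + 0.842) / √(n − 3 − 4)]. At n = 90 this is tanh(2.802/√83) = 0.30. Simulation gives about 0.30 at n = 90, and about 0.33, 0.36 and 0.42 at n = 75, 60 and 45; the approximation agrees to within 0.01. The smaller numbers are an assumed range for DPDD, since a person who does not drink in the quit week has no drinking day to average.

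**The case against.** The strongest defence is that the drug-minus-placebo wording is shorthand. Aims 1 and 2 use the same pairings as between-subject contrasts, and each participant does have a Day 1 and a Day 14 cue score. A participant-level model with arm terms would therefore be computable and would fit the stated intent. The plan already contains templates: mediation for Secondary Aim 1 (section 3.2.4) and medication as moderator for Secondary Aim 2 (section 3.2.5). This stands as far as it goes, and it is why the aim can be rescued. But neither template is written for Aim 3, and section 3.2.3 names the drug-minus-placebo scores themselves as the variables on both sides.

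A reader might infer three stronger things that the documents do not support.
- That Aim 3 cannot be run at all. Readings 2 to 4 can be computed; they fail because they do not address the aim, and the text does not choose among them.
- That the rates under Reading 4 are false-positive rates. They are power to detect a person-level association. They mislead only if that association is reported as a link between drug effects.
- That the trial's main efficacy results are in doubt. Aims 1 and 2 do not use section 3.2.3.

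It is also fair to say that any replacement involves choices. What is needed is one participant-level model stated in advance; the model below is a reasonable choice, not the only one.

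**Conclusion.** The point holds, and section 3.2.3 should be corrected before unblinding, because it is a primary aim and the correction is cheap. The defect is structural: it follows from the parallel design and the definition of the scores, and rests on no assumed effect size. No other section repairs it.

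The degrees-of-freedom results are exact; the zero-df statement assumes a fitted intercept. The significance rates under Reading 4 depend on assumed correlations of 0.2 to 0.4, on 30 completers per arm, and on whether the drugs are pooled. The detectable correlations depend on how many participants have a DPDD value. That the wording was carried over from a crossover design would be a natural guess, but the documents do not say so and the conclusion does not need it.

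**What to change.** Before unblinding, replace section 3.2.3 with the following.

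- **Model.** Regress each quit-week outcome (PDA and DPDD) on the participant's Day 14 AUQ alcohol-minus-water score, adjusted for the Day 1 AUQ alcohol-minus-water score, the matching baseline drinking measure and medication arm. Add an arm-by-craving interaction as a check on the common slope, in line with the moderator model of section 3.2.5.
- **Interpretation of the slope.** Report it as a concurrent person-level association only. It too will often be significant with no drug effect, in about 81% of trials at a partial correlation of 0.3 with 90 completers.
- **Medication link.** For each drug versus placebo, report the arm effect on Day 14 cue reactivity multiplied by that slope, with a bootstrap interval. Section 3.2.4 already uses mediation. Label the product exploratory and non-causal: cue reactivity is not randomized, and it is measured on Day 14, after Days 8–13 of the quit week, so drinking in that week could drive Day 14 craving.
- **Arm level.** Show the two contrast pairs descriptively, without a test.
- **Data Analytic Plan introduction.** Delete medication order from the covariate list.

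The cost is wording only, with no new data or participants. The price is limited precision: 80% power needs a partial correlation of about 0.30 at n = 90, rising to about 0.33, 0.36 and 0.42 if only 75, 60 or 45 participants have a DPDD value. The plan should also accept that the medication link becomes exploratory, and that a non-zero product would not by itself validate the paradigm.
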